6.6.5. Context and rationale for outcome(s) of interest

The primary outcome for the database study was defined to emulate the primary outcome for the trial, time from index to death due to any reason (overall survival). Operational definitions:

- EDB1: Time in {days, months and years} from index date to death due to any reason. The date of death is de-identified to month-level granularity or (rarely) to year-level granularity and the date of death is therefore imputed to the 15th of a month or mid-year/July 2 of the year of death, respectively. In If there is no indication that a patient died during the study period, the patient is censored. The censoring date is defined as the last visit or treatment encounter or data cut-off date, whichever occurred earlier. The overall survival endpoint is operationalized using a parameterized R function edb1_get_os() and more details can be found in the attached pdf documentation.
- EDB2: Time in {days, months and years} from index date to death due to any reason. If there is no indication that a patient died during the study period, the patient is censored. The censoring date is defined as the last observed activity date or data cut-off date, whichever occurred earlier. Activity dates are defined as documented in Table 4. Dates used to derive time to all-cause mortality may have some associated imprecision such that the date of death is either known completely, the year and month is known or only the year is known. The overall survival endpoint is operationalized using a parameterized R function edb2_get_os() and more details can be found in the attached pdf documentation.

Table 4. Relevant clinical activities considered to derive last activity date for censoring.

Table / clinical activity considered	Dates considered
Adverse events	Event date
Therapy (cellular, systemic, radiation, surgery)	Start and end dates or declined intervention date, surgery date, assessed resection dates
Palliative care referral	Referral date
Visits	Contact/visit date
Vitals	Assessed date
Labs	Lab date
Biomarkers	Specimen collection date
Patient observation period	Start and end dates
Demographics	Date of most recent contact with provider, date patient was diagnosed with a second primary malignancy
Performance assessments	Documented date, reported date

[figure not shown]
Secondary diagnoses	Diagnosis date
Progression, histology, lymphovascular invasion, metastatic sites, pancoast tumor, perineural invasion	Assessed date
Stage/TNM	Assessed date
Smoking	Assessed date

• EDB4: Time in {days, months and years} from index date to death due to any reason. The date of death is de-identified to month-level granularity and the day of death is therefore imputed to the 15th of a month. If there is no indication that a patient died during the study period, the patient is censored. The censoring date is defined as the last date of vital signs recorded as proof that the patient was alive at that time (de-identified to week-level granularity) or data cut-off date, whichever occurred earlier. The overall survival endpoint is operationalized using a parameterized R function edb4_get_os() and more details can be found in the attached pdf documentation.

6.6.6. Context and rationale for follow up

Only intention-to-treat (ITT) analyses will be conducted. Although cross-over from the exposure to the comparator can be expected which biases the exposure treatment effect more towards the null, this also applies to the RCT. According to Ramalingam et al.6, 65% of patients allocated to the standard of care arm received a subsequent antineoplastic therapy following erlotinib or gefinitib discontinuation (Figure 3). Out of these 65%, almost half (47%) crossed over to receive osimertinib. An as-treated analysis is not considered since in the context of oncology, reasons for discontinuation usually are due to toxicity, death or progression/non-response to the current treatment, all of which are highly correlated with the outcome under study which would hence lead to bias due to informative censoring.

Figure 3. Illustration of proportion of patients who received a first subsequent therapy after discontinuation of their assigned treatment. Taken from N Engl J Med 2020;382:41-50⁶

6.6.7. Context and rationale for covariates

We identified a series of covariates that are strong prognostic factors for the outcome and auxiliary covariates which may be useful to impute missing data. Such covariates comprise demographics, covariates indicating disease-severity, cancer-specific covariates as well as pathological and genetic factors. In addition, selected labs and vitals are considered since they were shown to carry a high amount of prognostic information as described in Becker, Weberpals, et al.¹⁰ For these variables, additional plausibility checks and transformations are carried out. In detail, labs and vitals are individually checked if they cross a certain biologically implausible threshold (e.g., a heart rate of 0) in which cases the values are set missing and imputed in a next step. These thresholds were compiled by experienced practicing physicians and medical oncologists and are listed in appendix **Table 10** and **Table 11**.

Note that not all covariates are available across all databases used for this trial emulation. In the analytical stage, the most comprehensive model will be fit for each database individually.

Table 5. Operational definitions of key covariates used for trial emulation.

Characteristic	Harmonized analysis variable name	R function to derive covariate (see pdf in appendix)	Details ¹	Variable encoding	Assessment window
Age at initial diagnosis	dem_age_initial_diagnosis	edbx_get_demographics()	Age measured at initial diagnosis of eligible primary tumor	Nominal (<60, 60-69, 70-79, 80+)	[-inf;0] at initial diagnosis of primary cancer
Age at index date	dem_age_index	edbx_get_demographics()	Age measured at index date	Binary (<60, 65+); modelled continuously in ROPRO ¹⁰	[0;0]
Sex	dem_sex	edbx_get_demographics()	Sex	Binary (Male, Female)	[0;0]
Year of index date	c_year_index	De novo derived from dt_index	Calendar year in which patient initiated study treatment	Nominal (<2018, 2018+)	[0;0]
Family history	dem_family_history	edbx_get_demographics()	Family history of cancer	Logical (TRUE, FALSE)	[0;0] (no specific date is associated)
Race	dem_race	edbx_get_demographics()	Race categorized as in the original RCT	Binary (Asian vs non-Asian)	[0;0]
Ethnicity	dem_ethnicity	edbx_get_demographics()	Ethnicity	Hispanic, Non-Hispanic	[0;0]
Region	dem_region	edbx_get_demographics()	US region patient receives care in; if given on a state level, region is manually mapped (see	Nominal (Northeast, South, West, Midwest)	[0;0]
			Table 12)		
Practice type	dem_practice	edbx_get_demographics()	Setting patient is receiving care at	Nominal (academic, community, academic & community)	[-inf;0]
Socio-economic status	dem_ses	edbx_get_demographics()	Socioeconomic status (SES) index based on residence area of patient	Nominal (from '1 - Lowest SES' through '5 - Highest SES)	[-inf;0]
Smoking	c_smoking_history	edbx_get_demographics()	History of current or former (= TRUE) or never (= FALSE) smoking on or anytime before index date; if there are multiple records per patient, any evidence of former/current smoking is prioritized	Binary logical (TRUE, FALSE)	[-inf;0]
EGFR status	C_egfr_biomarker_status	edbx_get_biomarker()	Evidence of any EGFR mutation present. If patient has multiple measurements, any evidence of a mutation is prioritized. In case of ties, the closest measurement relative to index date is selected	Binary (negative, positive)	[-180;0]

Characteristic	Harmonized analysis variable name	R function to derive covariate (see pdf in appendix)	Details ¹	Variable encoding	Assessment window
ECOG	c_ecog	edbx_get_ecog()	ECOG performance status measured closest to index date within assessment window. In case of ties, the lower ECOG value is selected	Nominal (0, 1, 2, 3, 4); modelled as ordinal numeric in ROPRO ¹⁰ ; due to I/E criteria ECOG is modelled as a binary (0, 1) covariate	[-90;0]
Stage	c_stage_initial_dx	edbx_get_diagnosis_solid()	AJCC summary group stage at initial diagnosis	Ordinal numeric (from 0 to IV with sub-categories, e.g., IA1) ¹⁰	[-inf;0] at initial diagnosis of primary cancer
De novo metastatic status	c_de_novo_mets_dx	edbx_get_diagnosis_solid()	Evidence of presence of one or multiple metastases at/before initial diagnosis	Binary logical (TRUE, FALSE)	[-inf;0] at initial diagnosis of primary cancer
Evidence of metastases between initial diagnosis and index date	c_met_pre_index	edbx_get_diagnosis_solid()	Evidence of any metastasis between initial diagnosis and index date (includes the initial diagnosis and index date)	Binary logical (TRUE, FALSE)	[-initial dx;0]
Number of metastatic sites	c_number_met_sites	edbx_get_diagnosis_solid()	Number of metastatic sites for a given patient before/on index date	Integer	[-inf;0]
Time between initial diagnosis to index date	c_time_dx_to_index	edbx_get_diagnosis_solid()	Time in days between initial diagnosis to index date	Continuous	[-initial dx;0]
Time between earliest evidence of a metastatic and index date	c_time_met_dx_to_index	edbx_get_diagnosis_solid()	Time in days between earliest evidence of a metastatic and index date	Continuous	[-inf;0]
Histology (adenocarcinoma)	c_histology_match	edbx_get_histology()	Evidence of adenocarcinoma histology (non-squamous cell for EDB1)	Binary logical (TRUE, FALSE)	[-inf;0]
Albumin	c_albumin_g_l_cont	edbx_get_labs()	Closest albumin measurement (in serum/plasma) relative to index date in g/L. In case of ties, the lower is selected	continuous	[-90;0]
Alkaline phosphatase (ALP) ²	c_alp_u_l_cont	edbx_get_labs()	Closest alkaline phosphatase measurement (in serum/plasma) relative to index date in U/L. In case of ties, the lower is selected	continuous	[-90;0]
Alanine aminotransferase (ALT) ²	c_alt_u_l_cont	edbx_get_labs()	Closest alanine transaminase measurement (in serum/plasma) relative to index date in U/L. In case of ties, the lower is selected	continuous	[-90;0]

Characteristic	Harmonized analysis variable name	R function to derive covariate (see pdf in appendix)	Details ¹	Variable encoding	Assessment window
Aspartate aminotransferase (AST)	c_ast_u_l_cont	edbx_get_labs()	Closest aspartate aminotransferase measurement (in serum/plasma) relative to index date in U/L. In case of ties, the lower is selected. Used to compute AST-ALT ratio	continuous	[-90;0]
AST/ALT ratio	c_ast_alt_ratio_cont	edbx_get_labs()	AST/ALT ratio calculated from c_ast_u_l_cont/c_alt_u_l_cont	continuous	[-90;0]
Bilirubin ²	c_bilirubin_mg_dl_cont	edbx_get_labs()	Closest bilirubin measurement (in serum/plasma) relative to index date in mg/dL. In case of ties, the lower is selected	continuous	[-90;0]
Calcium ²	c_calcium_mg_dl_cont	edbx_get_labs()	Closest calcium measurement (in serum/plasma) relative to index date in mg/dL. In case of ties, the lower is selected	continuous	[-90;0]
Chloride	c_chloride_mmol_l_cont	edbx_get_labs()	Closest chloride measurement (in serum/plasma) relative to index date in mmol/L. In case of ties, the lower is selected	continuous	[-90;0]
Eosinophils/100 leukocytes ²	c_eosinophils_leukocytes_r atio_cont	edbx_get_labs()	Eosinophils/100 leukocytes in blood. In case of ties, the lower	continuous	[-90;0]
Glucose ²	c_glucose_mg_dl_cont	edbx_get_labs()	Closest glucose measurement (in serum/plasma) relative to index date in mmol/L. In case of ties, the lower is selected	continuous	[-90;0]
Hemoglobin	c_hemoglobin_g_dl_cont	edbx_get_labs()	Closest hemoglobin measurement (in blood) relative to index date in g/L. In case of ties, the lower is selected	continuous	[-90;0]
Lactate dehydrogenase (LDH) ³	c_ldh_u_l_cont	edbx_get_labs()	Closest LDH measurement (in serum or plasma) relative to index date in U/L. In case of ties, the lower is selected	continuous	[-90;0]
Lymphocytes	c_lymphocyte_10_9_I_cont	edbx_get_labs()	Closest lymphocytes measurement (in blood) relative to index date in 10°/L. In case of ties, the lower is selected. Used to compute neutrophil/lymphocyte ratio	continuous	[-90;0]

Characteristic	Harmonized analysis variable name	R function to derive covariate (see pdf in appendix)	Details ¹	Variable encoding	Assessment window
Lymphocyte/leukocyt e ratio ²	c_lymphocyte_leukocyte_ra tio_cont	edbx_get_labs()	Closest lymphocyte/leukocyte ratio measurement (in blood) relative to index date. In case of ties, the lower is selected. Used to compute neutrophil/lymphocyte ratio	continuous	[-90;0]
Monocytes ²	c_monocytes_10_9_I_cont	edbx_get_labs()	Closest monocytes measurement (in blood) relative to index date in 109/L. In case of ties, the lower is selected.	continuous	[-90;0]
Neutrophils	c_neutrophil_10_9_l_cont	edbx_get_labs()	Closest neutrophils measurement (in blood) relative to index date in 10°/L. In case of ties, the lower is selected. Used to compute neutrophil/lymphocyte (NLR) ratio	continuous	[-90;0]
Neutrophil/lymphocyt e ratio ²	c_neutrophil_lymphocyte_r atio_cont	edbx_get_labs()	Neutrophil/lymphocyte (NLR) ratio calculated from c_neutrophil_10_9_l_cont/ c_lymphocyte_10_9_l_cont	continuous	[-90;0]
Platelets	c_platelets_10_9_l_cont	edbx_get_labs()	Closest platelets measurement (in blood) relative to index date in 109/L. In case of ties, the lower is selected	continuous	[-90;0]
Protein	c_protein_g_l_cont	edbx_get_labs()	Closest protein measurement (in serum/plasma) relative to index date in g/L. In case of ties, the lower is selected	continuous	[-90;0]
Urea nitrogen ²	c_urea_nitrogen_mg_dl_co nt	edbx_get_labs()	Closest urea nitrogen measurement (in serum/plasma) relative to index date in mg/L. In case of ties, the lower is selected	continuous	[-90;0]
Systolic blood pressure ²	c_sbp_cont	edbx_get_vitals()	Closest systolic blood pressure (in mmHg) measurement. In case of ties, the lower is selected	continuous	[-90;0]
Body mass index (BMI) ²	c_bmi_cont	edbx_get_vitals()	Closest BMI measurement (in kg/m²) relative to index date. In case of ties, the lower is selected. For ROPRO and in EDB2, BMI is (additionally) computed from individual height and weight measurements	continuous	[-90;0]

Characteristic	Harmonized analysis variable name	R function to derive covariate (see pdf in	Details ¹	Variable encoding	Assessment window

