The purpose of this protocol is to describe the emulation of the **FLAURA trial**.^{5,6} FLAURA was a Phase III, double-blind, randomised study assessing the efficacy and safety of AZD9291 (= osimertinib, 80 mg orally, once daily) versus a standard of care (SoC) Epidermal Growth Factor Receptor (EGFR) Tyrosine Kinase Inhibitor (TKI) (either gefitinib [250 mg orally, once daily] or erlotinib [150 mg orally, once daily]) in patients with locally advanced or metastatic EGFR sensitizing mutation (EGFRm+) Non-small Cell Lung Cancer (NSCLC) who are treatment-naïve and eligible for first-line treatment with an EGFR-TKI.

The primary trial estimate targeted for emulation is a hazard ratio (HR) for death (overall survival) of 0.80 (95% CI 0.64 to 1.00) with a median overall survival time of 38.6 months (95% CI 34.5 to 41.8) in the osimertinib group and 31.8 months (95% CI, 26.6 to 36.0) in the comparator group. Market availability of osimertinib began April 18, 2018 based on the progression-free survival (PFS) endpoint.

The PFS endpoint was published in the NEJM on November 18, 2017 (PMID 29151359).5

The OS endpoint was published in the NEJM on November 21, 2019 (PMID 31751012).6

5. Research question and objectives

The primary and secondary research question is summarized in Table 1.

A. Primary research question and objective

Table 1. Primary and secondary research questions and objective.

Objective:	To compare the overall survival [OS] in patients who initiated osimertinib versus patients who initiated erlotinib or gefitinib.			
Hypothesis:	Initiation of osimertinib improves overall survival time as compared to initiation of erlotinib or gefitinib			
Population (mention key inclusion-exclusion criteria):	 Age at least 18 years Locally advanced or metastatic Non-small Cell Lung Cancer (NSCLC) patients who receive treatment without curative intent The line of therapy for patients in EDB1 and EDB2 is implicitly advanced/metastatic because the line of therapy classification starts after their advanced/metastatic diagnosis in the respective database In EDB4, patients must explicitly have any evidence of a metastasis prior initiating Osimertinib, gefitinib or erlotinib. 			

	Adenocarcinoma histology		
	EGFR sensitizing mutation (any EGFRm+)		
	Treatment-naïve and eligible for first-line (1L) treatment with an EGFR-targeted tyrosine kinase inhibitor (TKI)		
	• ECOG 0 or 1		
Exposure:	Initiation of osimertinib		
Comparator:	Initiation of erlotinib or gefitinib		

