Table 7. Primary and subgroup analysis specification

able 7. Primary and Subgroup	7 dilarysis specification
Hypothesis:	Initiation of osimertinib decreases the hazard of all-cause mortality as compared to initiation of erlotinib or gefitinib
Exposure contrast:	Initiation of osimertinib vs. initiation of erlotinib or gefitinib
Outcome:	Time to all-cause mortality (overall survival)
Databases used:	EDB1
Analytic software:	R 4.3.2. Version control of code and R packages will be established through git and Posit package manager, respectively. All packages are frozen to their most recent version as of April 24, 2024.
Model(s): (provide details or code)	See example code https://drugepi.gitlab-pages.partners.org/encore/flaura-nct-02296125/ (access only through MGB network for authorized personnel)
Confounding adjustment method	Name method and provide relevant details, e.g. bivariate, multivariable, propensity score matching (specify matching algorithm ratio and caliper), propensity score weighting (specify weight formula, trimming, truncation), propensity score stratification (specify strata definition), other. 1:1 propensity score nearest neighbor matching without replacement and a caliper of 1% of propensity score standard
Ministration of the	deviation
Missing data methods	Name method and provide relevant details, e.g. missing indicators, complete case, last value carried forward, multiple imputation (specify model/variables), other.
	Multiple imputation by chained equations using a random forest imputation model across all covariate types. The number of imputed datasets will be determined by the average proportion of missing values across all partially observed covariates. Imputation models will include all variables of the substantiative model, i.e., exposure, outcome, confounders/prognostic factors and additional auxiliary covariates.
Subgroup Analyses	List all subgroups
	In subgroup analysis, multiple imputation, propensity score matching and balance assessment will be conducted within each subgroup separately. The treatment effect will be estimated in the combined dataset by fitting a Cox proportional-hazards model that will include the exposure, the subgroup covariate of interest, and the treatment-by-subgroup interaction term. 1. Sex (Male, Female)
	2. Age (<65, ≥65)* 3. Resp (athricity (Agian Non Agian)*
	3. Race/ethnicity (Asian, Non-Asian)*4. Smoking history (current/former, never)5. ECOG (0, 1)*

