Sensitivity #1	Caliper matching on ROPRO prognostic score instead of propensity score	Matching patients on validated prognostic score may be more beneficial to control for (unmeasured) confounding	Matches patients on validated prognostic score that incorporates weights of key prognostic factors	Limited experience on how to optimally use prognostic scores and should be seen as an experimental sensitivity analysis
Sensitivity #2	ATO weighting instead of matching	Weights that resemble the average treatment effect in the overlap population (ATO) create a clinical equipoise population which is comparable to an RCT	ATO weighting usually results in excellent balance and clinical equipoise	Estimates the average treatment effect among the overlap patients which may not be comparable to target population anymore
Sensitivity #3	SMR/ATT weighting instead of matching. Here symmetric trimming (i.e., setting all weights lower/higher than that at a given quantile to the weight at the quantile) of extreme weights may be considered with the quantiles chosen based on weight distribution and resulting balancing performance.	SMR weighting retains all patients and resembles the same estimand as matching	ATT weighting retains all patients	Patients with extreme weights after trimming may bias the analysis
Sensitivity #4	Censoring date is changed to 3 months before data cut- off date	For all databases, information on mortality comes from different data sources which are updated asynchronously. To account for the potential lag of updated mortality information (ghost-time	Approach implements a more conservative censoring rule	Approach addresses ghost-time bias by censoring patients without a recorded

		bias ³³), the censoring date for patients without mortality event in the whole patient identification period will be moved to last sign of patients being alive/visit or 3 months before data cut-off date, whichever occurred earlier. ³⁴		death event earlier
Sensitivity #5	Delta imputation models for MNAR (tipping point analysis)	Primary multiple imputation analysis assumes MAR which may not hold for every covariate	Estimates impact of deviations from MAR assumption on final treatment effect estimates for key covariates	Delta parameters must be assumed and results are complex to interpret in multivariate missingness settings; just must important covariates or those with highest suspicion of being MNAR will be evaluated

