10.3. Sample size/power calculations

Power estimations are computed based on the average number of observed events across imputed and matched datasets according to the methodology described by Schoenfeld.³⁵ Considering EDB1 only for primary analysis and assuming a HR = 0.8 and an alpha = 0.05 (2-sided), this results in an estimated statistical power (1-estimated type II error) of 80%.

Figure 12. Number of events needed to achieve x% power.

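### Table 5 codes age at index as under 60 or 65+, which leaves ages 60-64 in no category and disagrees with the 65-year split in Table 7

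*Protocol*

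**What the plan says.** Protocol section 6.6.7 introduces its covariates with "We identified a series of covariates that are strong prognostic factors for the outcome", together with auxiliary variables for imputation. Table 5 is titled "Operational definitions of key covariates used for trial emulation", so its encoding column is meant to be implemented.

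- **Age at index date** (`dem_age_index`): "Binary (<60, 65+); modelled continuously in ROPRO".
- **Age at initial diagnosis**, the row above: "Nominal (<60, 60-69, 70-79, 80" and over, which is four adjoining bands.
- **Age subgroup** (section 6.7.1, Table 7): two groups, under 65 and 65 or over, marked as a subgroup where FLAURA showed a significant difference.
- **Eligibility** (section 5, Table 1): "Age at least 18 years", so patients aged 60 to 64 are in the study population.
- **Primary adjustment** (Table 7): "1:1 propensity score nearest neighbor matching without replacement and a caliper of 1% of propensity score standard" deviation.
- **Sensitivity analysis #1** (Table 9): "Caliper matching on ROPRO prognostic score instead of propensity score". This is the only analysis for which the readable text says that age is used as a continuous value.

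**The concern.** A binary covariate must place every eligible patient in one of two levels, and this one does not. A 62-year-old has a known age but no assigned level. A programmer could read the cell as <65 / ≥65, as <60 / ≥60 (which would match the first band edge in the row above), or literally. The first two give different covariates. The third turns a known age into a missing value.

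Several analyses depend on the reading. Age is a candidate for the primary propensity score. The complete-case analysis (#12) names age among the key covariates with little missingness, so if index age is the variable meant, a literal coding would remove patients aged 60 to 64. The re-weighting to FLAURA (#7) refers to the Table 7 effect modifiers and needs an unambiguous age split.

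A second, lesser weakness remains after the gap is closed. Two bands treat a 66-year-old and an 85-year-old as equal on index age, and a standardised difference computed on the binary variable cannot show imbalance within a band. The same cell shows that the continuous value exists, and Table 5 lists labs, vitals and times since diagnosis as continuous.

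**Working it through.** The protocol gives no figure for this point that could be reproduced. The check has three steps.

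**1. Which ages are uncovered**

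Testing each whole age from 18 to 99:

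| Coding | Ages in no level |
|---|---|
| <60, 65+ (Table 5) | 60, 61, 62, 63, 64 |
| <65, ≥65 (Table 7) | none |

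This step needs no assumption.

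**2. How many patients that would be**

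The readable text gives no age distribution. Assume normal ages with mean μ from 63 to 72 and SD σ from 10 to 12. The share in the gap is Φ((65 − μ)/σ) − Φ((60 − μ)/σ).

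- μ = 63, σ = 10: Φ(0.20) − Φ(−0.30) = 0.579 − 0.382 = 0.197
- μ = 68, σ = 11: Φ(−0.27) − Φ(−0.73) = 0.159
- μ = 72, σ = 12: Φ(−0.58) − Φ(−1.00) = 0.280 − 0.159 = 0.121

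The range is about 12-20%.

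**3. What banding costs once the gap is closed**

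Assumed inputs, none from the protocol:

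- age is normal with mean 68 and SD 11;
- the log odds of receiving osimertinib change by 0.1 to 0.3 per 10 years of age;
- the log hazard of death rises by 0.2 to 0.3 per 10 years.

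Under this model the unadjusted age difference between arms is about 1.2 years (log OR 0.1) to 3.5 years (log OR 0.3). Stratifying on age bands removes part of it. The bias in the HR is exp(log HR per 10 years × remaining years / 10) − 1.

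| Age term | Share of difference left | Remaining years | HR bias, smallest to largest |
|---|---|---|---|
| Two bands, cut at 65 | 37-38% | 0.46 to 1.35 | exp(0.2 × 0.046) − 1 = 0.9% to exp(0.3 × 0.135) − 1 = 4.1% |
| Four bands, cut at 60, 70, 80 | about 12% | 0.15 to 0.43 | exp(0.2 × 0.015) − 1 = 0.3% to exp(0.3 × 0.043) − 1 = 1.3% |
| Continuous | almost none | about 0 | about 0 |

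As a cross-check, the share left should be close to the share of age variance that the bands do not explain. At mean 68 and SD 11 a cut at 65 explains 63% (37% left) and four bands explain 88% (12% left).

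The four-band row uses bands of index age as a stand-in for the Table 5 bands of age at diagnosis. A simulation with both age variables, allowing up to half of patients a longer interval from diagnosis to index (assumed exponential, mean 2 years) and a treatment log OR of 0.2 per 10 years, left about 10-17% of the difference and an HR bias of about 0.5-1.0%. This agrees with the four-band row.

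**The case against.** The strongest reply is that the gap is a one-character slip. The cell says binary, its upper level equals the Table 7 cut, and the protocol has no other two-level age split. Reading the lower level as under 65 removes both the gap and the conflict. This is the likely explanation. It does not settle the matter, because Table 5 is the operational definition and nothing in it or elsewhere states that reading.

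A reader might infer that patients aged 60 to 64 will have their age set to missing and imputed. The documents do not support that. Section 6.6.7 sets values to missing only for implausible labs and vitals, and the function that derives age is not visible. The loss occurs only if the cell is coded as printed.

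A reader might also infer that the primary estimate carries age confounding of up to 4%. That would require two-band index age to be the only age term in the propensity score. The readable text does not list the propensity score terms, and the balance figures are not shown. Section 6.6.7 also says that each database gets the most comprehensive model available. If so, the four-band age at diagnosis and the continuous time from diagnosis to index would enter too, and together they carry most of the information on index age. This part of the objection stands in full, and it moves the expected size to the four-band row.

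Finally, banded age is common in propensity models, and sensitivity analysis #1 uses continuous age through ROPRO. Both are true. The second is a check outside the primary analysis and does not replace a correct definition within it.

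**Conclusion.** The definitional error is certain and rests on no assumption: ages 60 to 64 have no level in Table 5, and Tables 5 and 7 disagree. Its effect depends on how the cell was coded. If the intended cut was 65 and was coded that way, no patient's age is lost. If it was coded literally, about 12-20% of patients would be affected, given the assumed age distributions.

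The case for continuous age is sound but modest. With four-band age at diagnosis also in the model, the residual bias is about 0.3-1.3% of the HR. At the target HR of 0.80, 1.3% moves the estimate by about 0.01 (0.80 × 1.013 = 0.810), which is small against the trial's interval of 0.64 to 1.00. The 1-4% range applies only to two-band index age as the sole age term. These sizes rest on the assumed age distribution, treatment log OR and death log HR. The direction of the bias depends on which arm is older, and the readable text does not say. The correction should be made because the text is wrong and the remedy costs almost nothing, not because the primary result is shown to be at risk.

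**What to change.** 1. In Table 5, correct the categorical coding of age at index to <65 / ≥65, in agreement with Table 7, and state that it serves subgroups and description.
2. Enter the continuous `dem_age_index`, for example as a spline, in the propensity score and imputation models, and report its balance on the continuous scale.
3. Confirm that the derivation code places patients aged 60 to 64 in the <65 level and sets no known age to missing.

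The cost is a table edit, a changed model term and a short code check. The continuous variable already exists, so no new data are needed.
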